4.9 Data Collection

Data will be collected by the research assistant at the index ED visit, and on follow-up visits (day 3, 7 and 14). Any paper files with identifying information will be kept separately and securely from all other study sites. These files will be kept in a locked filing cabinet in a locked office in an OHRI research office on F6 (Civic campus of The Ottawa Hospital). Data will be extracted from each record of treatment, which includes physician, nursing, consultant, triage, ambulance, and any consultation reports. This information will be obtained from hospital medical records (i.e. EPIC). Data will be entered into a secure web-based electronic data capture system. No identifying personal health information will be recorded into this system. Any potentially identifying information in the case record forms for each assessment plus the day 7 patient questionnaire are uploaded separately in the OHSN-REB application.

4.10 Data Management

The Ottawa Methods Centre will be responsible for creating and maintaining a secure web-based database (i.e. the electronic data capture system). The case record forms will be available in electronic format via the secure web-based database. The research assistant will then enter the relevant data directly into the secure web-based database. Paper copies of de-identified case record forms will be stored in a secure and locked filing cabinet on F6 (Civic campus) of the research floor at OHRI. A list of participant names and MRN will be kept in order to contact patients at day 7 and 14. This list will be kept on the TOH/OHRI cloud that is password protected with only the Principal Investigator and Research Assistant having access to the file. These files are kept separately from any de-identified study documents. All files will be destroyed after the required storage period according to TOH and OHRI policies.

4.11 Sample Size

For the full-scale trial, a minimum of 52 participants must be recruited annually per site (see Appendix). The Civic and General ED treats approximately 200 cellulitis patients with oral antibiotics annually.⁵ If at least 180 patients can be approached per site per year, a minimum of 29% (52 participants) must be recruited at each site to meet the feasibility target. Based on previous experience with similar trials, we anticipate being able to recruit up to 35% of eligible patients. With 180 patients approached at each site, a 90% two-sided confidence interval around the anticipated recruitment rate will have a total width of 0.12, i.e. a lower limit of 0.291 and an upper limit of 0.413. Because the lower limit excludes the minimum feasibility target of 29%, we can be 90% confident that the future trial is feasible. Thus, our target sample size is 64 patients across both campuses over six months.

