4.8.1 Feasibility Outcomes

The **primary feasibility outcome** is:

1. Patient recruitment rate (percentage of approached eligible patients who are successfully recruited) over 6 months. Our goal is to recruit at least 29% of eligible patients (see Sample Size)

The secondary feasibility outcomes are:

2. Ability to approach eligible patients (goal <10% missed)
3. Ability to blind patients using a questionnaire
4. Protocol adherence (i.e. fully adherent to allocated treatment for 7 days)
5. Loss to follow up at 14 days (goal <10% attrition)

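### Section 4.11 claims 90% confidence in feasibility from an interval around an assumed 35%; at a true 35% the lower limit clears 29% only about 53% of the time, and the 180 is not tied to the six-month pilot

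*Combined protocol and SAP*

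**What the plan says.** All of the sample-size reasoning is in section 4.11 of the combined protocol and SAP. In order:

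- Volume: "The Civic and General ED treats approximately 200 cellulitis patients with oral antibiotics annually".
- Requirement: "If at least 180 patients can be approached per site per year, a minimum of 29% (52 participants) must be recruited at each site".
- Expectation: "we anticipate being able to recruit up to 35% of eligible patients".
- Precision: "With 180 patients approached at each site, a 90% two-sided confidence interval around the anticipated recruitment rate will have a total width of 0.12", with limits of 0.291 and 0.413.
- Conclusion: "Because the lower limit excludes the minimum feasibility target of 29%, we can be 90% confident that the future trial is feasible".
- Target: "Thus, our target sample size is 64 patients across both campuses over six months".

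Section 4.8.1 makes the recruitment rate the primary feasibility outcome and sets the criterion as "Our goal is to recruit at least 29% of eligible patients (see Sample Size"). It mentions no confidence limit. Section 4.12 plans to report feasibility outcomes as proportions with two-sided 90% intervals and does not say which criterion decides feasibility. Section 4.1 sets the duration at six months.

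**The concern.** There are two faults.

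**The inference.** The interval is centred on a rate that was assumed, and assumed as an upper expectation. The sentence that follows drops this condition and treats the rate as if it had been observed. A reader will take it that the design gives a 90% assurance of showing feasibility, which it does not.

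**The denominator.** The 180 starts as a number per site and year, is then used per site with no period, and leads directly to a target for two campuses over half a year. The linking step is missing, and the text leaves open whether the 200 a year belongs to one campus or to both.

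This is the only justification given for the sample size, and it concerns the primary outcome of a pilot meant to inform a trial of 2552 participants (Appendix A).

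**Working it through.** **Inputs.** From section 4.11: 180 approached, anticipated rate 0.35, threshold 29% (52/180 = 0.289), two-sided 90% interval (5% in each tail), target 64. From section 4.1: six months.

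**1. Reproduce the stated interval.** 0.35 × 180 = 63. The exact (Clopper-Pearson) limits are the 0.05 quantile of Beta(x, n − x + 1) and the 0.95 quantile of Beta(x + 1, n − x). For x = 63 and n = 180 they are 0.2909 and 0.4128, a width of 0.122. This matches the plan.

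**2. Find the count that clears 29%.**

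| Recruited of 180 | Lower 90% limit | Above 29%? |
|---|---|---|
| 62 | 0.2857 | no |
| 63 | 0.2909 | yes |
| 64 | 0.2962 | yes |

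The anticipated rate is therefore exactly the minimum passing result; one patient fewer fails.

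**3. Chance of clearing it.** P(X ≥ 63), with X binomial (180, p):

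| True rate p | P(X ≥ 63) |
|---|---|
| 29% | 0.047 |
| 32% | 0.216 |
| 33% | 0.309 |
| 35% | 0.528 |
| 39.4% | 0.90 |

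Wald, Wilson, Agresti-Coull and Jeffreys intervals also need 63 and so give the same 0.528 at 35%. Wald with continuity correction needs 64 and gives 0.466.

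**4. The looser criterion.** If feasibility means only an observed rate of at least 29%:

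| Count required | Chance at true 35% | Chance at true 29% |
|---|---|---|
| 52 (as section 4.11 counts it) | 0.965 | 0.541 |
| 53 (29% applied strictly) | 0.951 | 0.476 |

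This criterion is easily met at 35%, but it is also met about half the time when the true rate only equals the threshold. Meeting it would not supply the claimed confidence either.

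**5. The denominator.** 180/200 = 0.90, which agrees with the secondary goal "Ability to approach eligible patients (goal <10% missed"). The 200 and the 180 therefore share a unit. Three readings follow:

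- *Literal, 180 at each of two campuses during the pilot:* 2 × 180 = 360 approached, and 0.35 × 360 = 126 recruited. This does not match 64.
- *200 a year per campus:* 2 × 180 × 0.5 = 180 approached in total, and 64/180 = 35.6%. This matches.
- *200 a year for both campuses together:* 180 × 0.5 = 90 approached in total, and 64/90 = 71.1%. This does not match an expectation of at most 35%. On this reading the interval at about 35% is roughly 0.27 to 0.44 (31/90: 0.261 to 0.435; 32/90: 0.272 to 0.447). At least 34 of 90 are needed (33/90 gives a lower limit of 0.2819, 34/90 gives 0.2922), and P(X ≥ 34) at a true 35% is 0.326.

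**The case against.** The strongest reply is that this is an ordinary precision-based design. The text says that the interval surrounds an anticipated rate, and the target of 64 comes next. If 64 of 180 are recruited, the lower limit is 0.296 and the claim is borne out. A chance of about one half is what one gets when the interval at the expected rate is made just to clear a threshold. Neither section 4.8.1 nor section 4.12 requires the lower limit to exceed 29%, and the goal as listed is met with probability 0.95 to 0.97 at a true 35%. The final conclusion will rest on the observed rate and its own interval.

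Much of this stands. The limits are right, the sentence is true conditionally, and the 0.53 applies to the rule that section 4.11 implies, not to one stated under outcomes. None of it rescues an unconditional claim of 90% confidence made before any patient has been approached.

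On the denominator, the reply is that the plan's own figures point to the per-campus reading: 90 approached per campus in six months, 35% of which is 31.5, rounded up to 32, gives 64 over two campuses. That is persuasive, and the reading with 90 approached in total is the less likely one. But the derivation has to be inferred, and the per-site wording of the interval is wrong for the pilot on this reading too.

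**Conclusion.** The concern holds. The interval is computed correctly; the conclusion drawn from it is wrong as written. With 180 approached, the chance that the lower limit exceeds 29% is about 0.53 at a true 35%. It is lower if the true rate falls short of what the plan gives as an upper expectation. These figures assume independent patients with a common recruitment probability, and the lower-limit rule implied by section 4.11. Under the observed-rate goal of section 4.8.1 the chance is about 0.97, and the plan does not say which rule decides.

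The target of 64 is probably sound: it fits a pooled six-month total of 180, which holds if the 200 a year is per campus. If the 200 covers both campuses, neither the interval nor the target fits the roughly 90 patients who could be approached. The point does not invalidate the pilot, but it should be corrected because it is the only support given for the sample size.

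**What to change.** In section 4.11:

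1. Replace the sentence claiming 90% confidence with a conditional one, for example: *If at least 63 of 180 approached patients are recruited, the lower limit of the two-sided 90% interval will exceed 29%; the probability of this is about 53% if the true rate is 35%.* The condition is necessary; giving the probability is recommended.
2. State whether the 200 patients a year is per campus or for both campuses.
3. If per campus, give 180 as the total across both campuses over six months, in place of the per-site wording, and show the step 2 × 180 × 0.5 = 180.
4. If both campuses together, restate the interval and the target for about 90 approached in total.

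It would also help to say in section 4.8.1 whether feasibility is judged on the observed rate or on the lower limit.

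On the per-campus reading the cost is two reworded sentences and one clarification, with no more patients and no change to the analysis. On the other reading the interval and target must also be reworked. Either way the stated assurance becomes less favourable.

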4.12 Data Analysis

Baseline demographic and clinical characteristics of participants will be described using descriptive statistics. Primary and secondary feasibility outcomes will be described using frequency and proportion with two-side 90% confidence intervals. Primary and secondary effectiveness outcomes will be described using frequency and proportion in each arm, together with 95% confidence intervals for the difference between the two arms. Analysis will proceed according to an intention-to-treat protocol.

While every effort will be made to avoid attrition, the prevalence of any missing data will be described in each arm and multivariable regression analysis will be used to identify baseline characteristics associated with attrition. Any identified characteristics will need to be adjusted for in the primary and secondary outcome analyses to avoid bias due to attrition. Single or multiple imputation will be used as sensitivity analysis to explore the implications of non-randomly missing data under extreme assumptions about attrition.

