4.8.2 Effectiveness Outcomes

The **primary effectiveness outcome** is:

1. **Oral antibiotic treatment failure**, defined as a change in antibiotic (change in class of oral antibiotic or step up to intravenous therapy) within 7 days due to worsening infection, which is defined as:
 - a. New fever (temperature $\geq 38.0^{\circ}\text{C}$) or *persistent* fever at Day 3 follow up; or
 - b. Increasing area of erythema $\geq 20\%$ from baseline; or
 - c. Increasing pain ≥ 2 points from baseline (numeric rating scale)

The secondary effectiveness outcomes are:

2. Clinical cure (no erythema, pain and fever) at day 7
3. Clinical response ($\geq 20\%$ reduction in area of erythema compared to baseline) at day 3
4. Adverse events (e.g. vomiting, diarrhea, rash) at 14-day telephone follow-up
5. Unplanned i) return ED visits; and ii) hospitalization at 14-day telephone follow-up

Baseline clinical data will be recorded at the index ED visit. Patients will be assessed at a home visit by the research assistant on: 1) Day 3 (mid-therapy); and 2) Day 7 (end-of-therapy). If criteria are met for worsening infection, they will be sent to the ED for evaluation. If a home visit is not possible, the following alternate methods of follow up will be offered to patients:

1. Video follow up via a mobile device (tablet or phone) using FaceTime, Zoom or Skype. The patient must own a mobile device with one of these applications in order to proceed with this option. If this option is chosen, the patient will be given a disposable tape measure and disposable temperature strip so that they can measure the dimensions of erythema and temperature, respectively during the video follow up. The patient will be asked to download a free mobile application (Preventicus Heartbeats; <https://www.preventicus.com/en/>) that will allow the patient to measure their heart rate at the time of follow up.
2. Return to the ED for assessment. In this case, hospital parking fees will be reimbursed for the patient

Study participants will complete a questionnaire on Day 7 regarding effectiveness of blinding, medication adherence and adverse events.

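### Section 4.12 lets a weak attrition screen pick the covariates for the effectiveness analyses; name one or two in advance instead

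*Combined protocol and SAP*

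**What the plan says.** Section 4.12 describes each effectiveness outcome as a frequency and proportion "in each arm, together with 95% confidence intervals for the difference between the two arms", under intention to treat. It then turns to attrition: "multivariable regression analysis will be used to identify baseline characteristics associated with attrition", followed by "Any identified characteristics will need to be adjusted for in the primary and secondary outcome analyses to avoid bias due to attrition". Imputation appears only as a sensitivity step: "Single or multiple imputation will be used as sensitivity analysis to explore the implications of non-randomly missing data under extreme assumptions about attrition".

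Section 4.12 does not give the candidate characteristics, the selection threshold, a limit on the number of covariates, the form of the adjusted model, or whether the simple or the adjusted difference is the main result. The SAP is part of this protocol, and no other section supplies these details.

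Three other sections set the scale. In 4.11, "our target sample size is 64 patients across both campuses over six months". In 4.8.1, the goal for loss to follow-up at 14 days is under 10%. In 4.8.2, failure is a change of antibiotic "within 7 days due to worsening infection". Section 4.7 stratifies the allocation by lower limb versus other location, and 4.12 does not mention that factor.

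**The concern.** The adjustment is worded as mandatory, and its content is decided by a regression with very few events. Such a screen can go wrong in two ways: it can miss the characteristic that really drives dropout, and it can pick one that has nothing to do with it. Because the threshold is not stated, two competent analysts could also report different adjusted differences from the same data.

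At stake is whether the pilot's failure difference can be reproduced, and whether the rule gives the protection against attrition bias that is its stated purpose. Section 3 makes preliminary evidence of effectiveness a specific goal, and section 5 says the results will inform the larger trial, so the estimate should be well defined even though it is imprecise.

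**Working it through.** **The plan's own figure.** Section 4.11 assumes 180 patients approached per site per year, so 90 per site in six months. 2 × 90 × 0.35 = 63, against the stated 64. The exact (Clopper–Pearson) 90% interval for 63/180 is 0.2909 to 0.4128, which matches the stated 0.291 and 0.413. The pilot size therefore reproduces to within one patient.

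**Inputs from the plan.** 64 patients (4.11); 1:1 allocation, so about 32 per arm (4.7); attrition goal under 10% (4.8.1); 20% failure on standard dose and a 5-point difference (Appendix A). **Assumed:** the threshold, the number of candidate covariates, the odds ratios, the prevalence of the factor and the dropout pattern.

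1. **Losses available to the screen.** 64 × 0.10 = 6.4, so 6 or fewer if the goal is met.

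2. **Chance of finding a real predictor at p<0.05, about 6 losses.**

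| Method | OR 3 | OR 5 |
|---|---|---|
| Simulation, 2–6 candidates, ordinary logistic | 16–21% | 26–35% |
| Simulation, 2–6 candidates, Firth | 21–25% | 40–45% |
| Exact, one factor of 50% prevalence (Fisher to likelihood ratio) | 9–27% | 19–46% |
| Exact, one factor of 30% prevalence (Fisher to likelihood ratio) | 20–27% | 39–48% |

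   At p<0.20 the likelihood-ratio test finds OR 3 in 51% (50% prevalence). With 10 losses OR 5 is found in 57–63% at p<0.05, so low power at OR 5 is confined to about 6 losses or fewer.

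3. **Noise and threshold.** When nothing predicts dropout and there are 6 losses, at least one of 2–6 candidates is flagged in 5–13% of trials (ordinary) or 7–19% (Firth). For longer lists of independent nominal tests, 1 − 0.95^k gives 23% for k = 5, 40% for k = 10 and 54% for k = 15. The ordinary fit fails (separation or no convergence) in 12–30% of these trials; Firth did not fail. Moving from p<0.05 to p<0.20 changes the flagged set in 22–41% (ordinary) or 28–59% (Firth).

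4. **Protection delivered in an unfavourable case.** Simulation: 32 per arm; a factor present in 30% of patients with failure 34% versus 14% (0.30 × 0.34 + 0.70 × 0.14 = 0.20); a 5-point effect; all 6 losses in one arm; OR 5 between factor and dropout.
   - Unadjusted bias: 1.3–1.5 points.
   - Always adjusting for two named covariates that include the factor: mean correction 1.37–1.43 points.
   - Screen-driven rule at p<0.05: 0.27–0.36 points (ordinary) or 0.40–0.47 (Firth). Shares run from 0.27/1.43 = 19% to 0.47/1.37 = 34%. Repeat simulations gave 21–31% (ordinary) and 37–41% (Firth).
   - Rule at p<0.20: about 60–65%.
   - With 10 losses: bias 2.1–2.7 points, share 35–50% at p<0.05.

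5. **Sensitivity to the dropout model.** Eight candidates, about 10% attrition, a continuous factor with OR 3 per SD for both dropout and failure, screen at p<0.05:
   - Dependence in one arm only: bias −1.42 unadjusted, −1.24 screened (13% removed), −0.17 with the factor named. A named list of three that omits the factor gives −1.41, with SD 0.101 against 0.099 unadjusted.
   - Opposite directions in the two arms: −2.5 unadjusted, −2.3 screened, +0.2 with the factor named; coverage 0.936, 0.936 and 0.944.
   - Same dependence in both arms: all within about 0.2–0.4 points, so there is nothing material to correct.

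6. **Size against sampling error.** The mean Miettinen–Nurminen 95% interval at 20% versus 15% with 32 per arm is 38.3 points wide. A 1.5-point bias is 1.5/38.3 = 4% of that. Coverage in the step 4 simulations stayed at 0.946–0.960 with 6 or 10 losses. When the Firth screen flags something at 6 losses, the estimate moves by a median of 1.1–1.4 points.

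7. **Missing outcomes.** If m patients lack failure status, the best-to-worst range of the difference is m/32: 2/32 = 6.3 points and 6/32 = 18.8 points, or 16% and 49% of the interval width.

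**The case against.** Several points on the other side stand.

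- **A comparison is already specified.** Section 4.12 does give a difference in proportions with a 95% interval. What it lacks is a ranking of that result against the adjusted one.
- **The screen does not look at the treatment effect.** It uses baseline data and dropout status. A reader might infer that choosing covariates after the fact biases the failure difference or invalidates its interval. The plan's text and the calculations do not support that: coverage with the screen was never materially below that of the unadjusted analysis. In the opposite-directions pattern both fell to 0.936, so attrition causes that dip and covariate selection does not.
- **Pre-naming is not better in every case.** A reader might infer that any fixed list beats the rule. It does not: a list that omits the driver is no better than no adjustment, and an estimate stratified by location alone kept the full 1.4-point bias when location was unrelated to dropout and failure, while the rule removed part of it.
- **The unfavourable case is extreme.** If dropout is unrelated to arm, all 6 losses fall in one arm with probability 2 × C(32,6)/C(64,6) = 2 × 906,192/74,974,368 = 2.4%, and the trial is blinded with identical capsules.
- **Six is not a firm count.** Under 10% is a 14-day goal and not a cap. Failure is a 7-day outcome, and the record extraction in 4.9 may recover some antibiotic changes, so the number missing for failure may differ.

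That this is a pilot lowers the stakes. It does not remove the need for a defined estimate, since evidence on effectiveness is one of its stated goals.

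**Conclusion.** The point holds, as a minor one. At the plan's own size and attrition goal the screen is too weak to do the job it is given, and its result depends on choices the text leaves open. The adjusted estimate is therefore not reproducible and carries only part of the intended protection. The share recovered rests on the assumed threshold and dropout model: 20–40% is the p<0.05 figure for six losses in one arm at OR 5, a looser cutoff recovers more, and the weaker continuous-factor model recovers less.

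The practical effect is small. Bias in the one-arm case is a few per cent of the interval width, and there is no material bias if dropout does not depend on arm. The opposite-directions pattern gives a larger bias, but it is a more extreme assumption. Recruitment and the other feasibility outcomes are single proportions and are unaffected. The finding does not show that the pilot's effectiveness result would be wrong, only that it is not fully defined in advance.

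**What to change.** In 4.12, replace the screen-driven adjustment with a pre-specified one:

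- Define the effectiveness result as the difference in failure with its 95% interval, accounting for location (lower limb versus other), for example by Mantel–Haenszel weighting.
- Report beside it a pre-specified version that also adjusts for one or two prognostic baseline measures named now, whether or not they turn out to be linked to attrition. Baseline erythema area and pain score are candidates, since the failure definition in 4.8.2 already requires them. Keep the list short: expected failures are 32 × 0.20 + 32 × 0.15 = 11.2.
- State which of the two is the main result, and name the adjusted model.
- Keep the attrition regression, and the summary of missing data by arm, as description only, with a small-sample method such as Firth.
- Report the already planned extreme-assumption analysis for 7-day failure as a best/worst-case table, read against the width of the pilot's interval.

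The cost is a few sentences and no new data. The downside is that the list corrects attrition bias only if it contains the factor behind dropout, and a list that misses it slightly widens the interval. Covariate adjustment also cannot repair missingness that depends on the unseen outcome, so the best/worst-case table is still needed. No gain in precision is claimed for stratifying by location; the reason is consistency with the randomisation.
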